	pregnancies complicated by IUGR. The CPR may predict adverse outcomes in low risk pregnancies. In a prospective study, we will examine whether fetuses with an abnormal CPR at or near term are at increased risk for being delivered by cesarean
Objective	To assess whether women with appropriately grown fetuses in otherwise low risk pregnancies with an abnormal CPR are more likely to be delivered by cesarean section
Endpoints	
Primary outcome variable:	Cesarean for non-reassuring fetal heart tracings
Secondary outcome variables:	Total cesarean delivery rate Umbilical cord blood pH Unidentified small for gestational age births Birthweight percentile Prevalence of category 2 or 3 fetal heart tracings Distribution of CPR by EFW Rate of operative vaginal delivery NICU admission Apgar scores at 1 and 5 minutes Composite neonatal outcome
Population	Healthy women with low-risk pregnancies receiving care at study institutions
Number of Sites enrolling participants	8
Description of Study Agent	Prenatal ultrasound Doppler assessment of the umbilical and middle cerebral arteries
Study Duration	12 months
Participant Duration	Between 1 day and 6 weeks

SCHEMATIC OF STUDY DESIGN

2 INTRODUCTION: BACKGROUND INFORMATION AND SCIENTIFIC RATIONALE

2.1 BACKGROUND

The CPR was first described in the 1980's. The CPR is calculated by dividing the Doppler indices of the middle cerebral artery (MCA) by the umbilical artery (UA). Most commonly, the pulsatility index (PI) is used to calculate the CPR. The CPR represents alterations in blood flow to the brain as a result of cerebrovascular dilation in response to hypoxia and increased placental resistance. The CPR has been best studied as a predictor of adverse pregnancy outcomes in fetus diagnosed with growth restriction. Newer studies have suggested the use of the CPR as an alternative approach for appropriately grown fetuses suffering from placental insufficiency who haven't reached their full growth potential but do not appear to be growth restricted (Morales-Rosello et al, Ultrasound Obstet Gynecol Jan 2015).

There is preliminary evidence that an abnormal CPR predicts adverse outcomes in otherwise low risk pregnancies. In a study by Prior et al. (Amer J Obstet Gyn February 2013) appropriately grown fetuses with an abnormal CPR (less than the 10th percentile) were 4 times more likely to be delivered by cesareansecondary to fetal distress in labor. A second study published by Morales-Roselló et al (Journal of Ultrasound in Obstetrics and Gynecology in

January of 2015) showed that appropriately grown fetuses with abnormal CPR were more likely to have lower cord blood gas pH levels.

The current standard of care is only to perform Doppler studies in growth restricted fetuses. Currently there is not data to support Doppler studies in the low risk obstetrical population. Our primary aim to investigate the value of assessing the CPR in fetuses that are at low risk for adverse outcomes.

While these limited data suggest that the CPR may be useful in predicting which women need cesarean and are at increased risk for abnormal fetal heart rate tracings and fetal acidosis, these data are only preliminary and further study is necessary.

2.2 RATIONALE

A major contributor to the increasing cesarean rate in the United States is abnormal fetal heart rate tracings leading to concerns for intrapartum hypoxia. Measuring the CPR close or at term may predict which fetuses are at greatest risk for fetal distress in labor and lead to better strategies to reduce the number of cesarean in this group. We aim to study whether an abnormal CPR in low risk women with normally grown fetuses predicts the need for cesarean and other adverse outcomes

2.3 POTENTIAL RISKS AND BENEFITS

2.3.1 KNOWN POTENTIAL RISKS

Women enrolling in the study will be having obstetric ultrasound ordered by their health care provider as part of their clinical care. The only additional intervention will performance of umbilical and middle cerebral artery Doppler studies at the time of this ultrasound. Because this study would not be performed as part of routine clinical care, providers caring for this patient will be blinded to the result of the study with the exception that the principal investigator deems that the pregnancy is at high risk for adverse outcome. Because providers caring for the patient will be blinded to the results, there should be no influence on the patient's care.

The only risk to study subjects is the inadvertent release of PHI, but safeguards will be put in place to minimize this risk.

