4 STUDY DESIGN AND ENDPOINTS

4.1 DESCRIPTION OF THE STUDY DESIGN

This is a multicenter prospective study of low-risk women who will be recruited if they are having an ultrasound at 36 weeks EGA or greater or if they are presenting to Labor and Delivery for induction of labor. As part of the study, women will have umbilical and middle cerebral artery Doppler studies and the CPR will be calculated by dividing the MCA PI by the UA/PI. Providers caring for study subjects will be blinded to this result. Pregnancy outcomes in women with CPR values less than the 10th percentile for gestational age will be compared to those with CPR values above the 10th percentile.

A secondary aim to our study is to analyze CPR as a continuous variable.

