5.4.2 HANDLING OF PARTICIPANT WITHDRAWALS OR TERMINATION

Participant withdrawals will be recorded and described in the final report of the study. Study data generated by a patient who has withdrawn will not be included in the final study of CPR effects on either the primary or secondary outcome variables.

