6 STUDY PROCEDURES AND SCHEDULE

6.1 STUDY PROCEDURES/EVALUATIONS

6.1.1 STUDY SPECIFIC PROCEDURES

- Study personnel will identify subjects who meet inclusion criteria and none of the exclusion criteria and approach them for informed consent to participate in the study.
- Once a subject agrees to participate, a brief obstetrical history will be obtained.
- If subjects' clinically indicated ultrasound study is normal, Doppler measurements of the umbilical and middle cerebral arteries will be obtained three times each and the mean value of the PI will be used to determine the CPR. Data will be recorded on study forms.
- The subject's medical record will be abstracted to obtain relevant data on study forms. Mode of delivery, whether this was a diagnosis of fetal compromise and managing physician's diagnoses will be obtained from the maternal chart. Birthweight, 1 and 5 minute Apgars scores, cord blood gasses (if done) and NICU admission will be recorded. The newborn birth record will also be reviewed for specific complications including need for supplemental oxygen, intracranial hemorrhage, hypoglycemia, jaundice, an unspecified complications.

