6.1.2 STANDARD OF CARE STUDY PROCEDURES

Standard of care will not be impacted by a subjects' enrollment in the study. The only difference in care will be assessment of the middle cerebral and umbilical artery by Doppler in women who consent to participate in the study. Clinical care providers will be blinded to the Doppler results. There will be no involvement of study personnel on Labor and Delivery. All data recorded for maternal and neonatal outcomes will be obtained by chart abstraction after delivery has occurred.

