6.3.7 SCHEDULE OF EVENTS TABLE

Procedures	Enrollment (Only Subject Visit)	Delivery Chart Abstraction	
Informed Consent	X		
Demographics	X		
Medical History			
Height			
Weight	X		
Middle Cerebral Artery Doppler	X		
Umbilical Artery Doppler	X		
CPR Calculation	X		
Maternal data		x	
Neonatal data		x	

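### Section 2.3.1 lets the principal investigator unblind care providers to the Doppler result but still concludes care is unaffected; other sections state blinding without exception, and no listed data item records a release

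*Protocol*

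**What the plan says.** Protocol section 2.3.1 says that providers are blinded to the study Doppler result "with the exception that the principal investigator deems that the pregnancy is at high risk for adverse outcome". It gives no criterion for that judgement. The next sentence reads "Because providers caring for the patient will be blinded to the results, there should be no influence on" the patient's care.

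Two other sections give the rule without the exception. Section 4.1: "Providers caring for study subjects will be blinded to this result". Section 6.1.2: "Clinical care providers will be blinded to the Doppler results"; it adds that enrollment leaves standard of care unchanged. Section 9.6.3, on breaking the blind, is marked as not applying.

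On data, section 6.1.2 says "All data recorded for maternal and neonatal outcomes will be obtained by chart abstraction after delivery has occurred". Section 6.1.1 lists mode of delivery, fetal compromise, the managing physician's diagnoses and neonatal items. The schedule in section 6.3.7 has one enrollment column and one headed "Delivery Chart Abstraction", with rows for maternal and neonatal data. Neither lists disclosure of a Doppler result.

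**The concern.** The study asks whether CPR predicts cesarean. The exception allows the exposure to reach the people who decide the outcome. Once a provider knows that a CPR is low, a later cesarean may be a response to the result, yet the analysis would count it as predicted by the result.

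The protocol does not say that the high-risk judgement rests on CPR. However, enrolled women are low risk, and study Dopplers are taken only if the "clinically indicated ultrasound study is normal, Doppler measurements of the umbilical and middle cerebral arteries will be obtained three times each". With a low-risk history and a normal scan, an abnormal Doppler is a plausible trigger, so releases may concentrate in the low-CPR group.

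The route is direct if the primary endpoint is any cesarean, as section 4.2.1 has it. It is weaker for the synopsis endpoint, cesarean for non-reassuring tracings, where knowledge of the result would act only through closer monitoring or a lower threshold for intervening in labor. In either case, releases not logged when they happen may not be reliably identifiable from charts later.

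**Working it through.** **Consistency of the text**

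| Section | Blinding of providers | Stated consequence |
|---|---|---|
| 2.3.1 | Yes, unless the principal investigator judges the pregnancy high risk | No influence on care |
| 4.1 | Yes, no exception | None stated |
| 6.1.2 | Yes, no exception | Standard of care unchanged |
| 9.6.3 | Breaking the blind does not apply | None stated |

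The conclusion in 2.3.1 needs complete blinding, which the preceding sentence has qualified.

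**Whether the withdrawal rules cover it.** Section 5.4.1 lets an investigator end participation when an exclusion criterion is newly met, and section 5.4.2 says "Study data generated by a patient who has withdrawn will not be included in the final study of CPR effects". A woman who develops preeclampsia or growth restriction can therefore leave the analysis. Low CPR is not an exclusion criterion in section 5.2, so a woman whose result was released for low CPR alone stays in.

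**The plan's own figure.** Section 9.5 gives 288 women with low CPR for 20% against 10%, 90% power and α = 0.05. Two-sided with equal groups:

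- Uncorrected: n = [1.960·√(2·0.15·0.85) + 1.282·√(0.20·0.80 + 0.10·0.90)]² / 0.10² = 266.
- Continuity-corrected: (n/4)·[1 + √(1 + 4/(0.10n))]² = 286.

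This agrees closely with 288, and the figure is not in dispute.

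**Size of a possible bias**

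Inputs from the protocol: about 300 low-CPR women among 3,000 (section 5.3), so 300 against 2,700; 10% cesarean in the higher-CPR group (section 9.5); chi-square test (section 9.1). Taken as two-sided at 0.05, without continuity correction.

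Assumptions: no true association, so 10% in both groups without release; release only in the low-CPR group; a fraction d released; a cesarean rate c among released women.

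Low-CPR rate = 0.10·(1 − d) + c·d. For example, d = 0.05 and c = 0.50 give 0.095 + 0.025 = 0.120. The false-positive rate comes from exact enumeration of the two binomials.

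| d (women released) | c | Low-CPR rate | Risk ratio | False-positive rate |
|---|---|---|---|---|
| 0 | – | 0.100 | 1.00 | 0.049 |
| 0.02 (6) | 0.20 | 0.102 | 1.02 | 0.053 |
| 0.02 (6) | 0.50 | 0.108 | 1.08 | 0.079 |
| 0.05 (15) | 0.20 | 0.105 | 1.05 | 0.063 |
| 0.05 (15) | 0.50 | 0.120 | 1.20 | 0.205 |
| 0.10 (30) | 0.60 | 0.150 | 1.50 | 0.732 |

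With equal release in both groups (d = 0.05, c = 0.50), both rates are 0.120 and the false-positive rate is 0.050.

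*Synopsis endpoint.* Assume a baseline b of 3% to 5%, with the risk in released women multiplied by m = 2 or 3. Rate = b·(1 − d) + m·b·d.

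- b = 0.03, d = 0.02, m = 2: rate 0.0306, false-positive rate 0.051.
- b = 0.05, d = 0.05, m = 3: rate 0.055, false-positive rate 0.076.

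*Scale.* Against 270/2,700, the smallest significant excess in the low-CPR group is 41/300. The pooled rate is 311/3,000 = 0.1037, so z = (0.1367 − 0.1000)/√[0.1037·0.8963·(1/300 + 1/2,700)] = 1.98. For 40/300, z = 1.80. The expected count is 30, so 11 extra cesareans are enough.

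**The case against.** The strongest case on the other side is that the mechanism is inferred. Section 2.3.1 ties the exception to a high-risk judgement and does not mention CPR. With equal release in both groups, the error rate does not move. Every release rate and every cesarean rate after release is assumed, and the scenarios run one way: some released women would have needed a cesarean anyway, and release could also lead to management that avoids one. If the planned effect is real, the conclusion holds: 5% released at a 50% cesarean rate moves 20% to 0.20·0.95 + 0.50·0.05 = 21.5%, a risk ratio of 2.15 instead of 2.0.

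Sections 4.1 and 6.1.2 can also be read as short statements of the general rule. The study forms are not shown and may hold a release field, the managing physician's diagnoses might reveal some releases, and a sensitivity analysis is normally SAP content.

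Most of this stands as a limit on size. It does not remove the defect. The no-influence conclusion contradicts the exception stated just before it, the withdrawal rules miss releases made for low CPR alone, and an SAP cannot analyze a release that was never recorded.

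**Conclusion.** The concern holds. The inconsistency is certain on the protocol text; the size of any bias is not known.

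For any cesarean as the endpoint, bias is small if releases are rare (false-positive rate 0.053 to 0.079 at 2% released). It is material if 5% are released and half of those women have a cesarean (0.205). It is severe only at the high end (0.73 at 10% released and 60% cesarean). For cesarean for non-reassuring tracings the range is 0.051 to 0.076. All these figures assume no true association and release confined to the low-CPR group.

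The lasting problem is that, as the protocol is written, nothing would show how many results were released or in which group. The point is worth correcting but does not by itself undermine the primary result. It concerns the protocol text only, since neither the study forms nor an SAP is shown.

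**What to change.** - State the exception in the same words in sections 2.3.1, 4.1 and 6.1.2, and align the entry in 9.6.3.
- Qualify or delete the sentence in 2.3.1 that concludes care is not influenced.
- Record every release on a study form when it happens: date, reason (including whether the Doppler prompted it) and recipient. Report counts by CPR group.
- In the protocol or SAP, add one sensitivity analysis of the primary outcome, shown two ways: excluding released women and, as a bound, counting their cesareans as non-events. Both are needed, because exclusion alone may remove women who were truly high risk.

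The release rule itself stays with the sponsor and the IRB. The cost is one short form entry, one extra analysis and wording in four sections; enrollment, sample size and care do not change.

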2.3.2 KNOWN POTENTIAL BENEFITS

Study subjects will not gain any benefit from enrolling in this observational study. Data gleaned from this work may be of benefit to pregnant women in the future.

3 OBJECTIVES AND PURPOSE

To determine whether the cerebroplacental ratio (CPR) performed after 36 weeks estimated gestational age predicts adverse obstetrical outcomes in low risk pregnancies

4 STUDY DESIGN AND ENDPOINTS

4.1 DESCRIPTION OF THE STUDY DESIGN

This is a multicenter prospective study of low-risk women who will be recruited if they are having an ultrasound at 36 weeks EGA or greater or if they are presenting to Labor and Delivery for induction of labor. As part of the study, women will have umbilical and middle cerebral artery Doppler studies and the CPR will be calculated by dividing the MCA PI by the UA/PI. Providers caring for study subjects will be blinded to this result. Pregnancy outcomes in women with CPR values less than the 10th percentile for gestational age will be compared to those with CPR values above the 10th percentile.

A secondary aim to our study is to analyze CPR as a continuous variable.

4.2.1 PRIMARY ENDPOINT

The primary endpoint is the cesarean delivery.

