4.2.2 SECONDARY ENDPOINTS

Secondary outcomes will be obtained by chart abstraction after delivery. These include the following:

- Total cesarean section rate
- Cord blood gases
- Cases of SGA undetected prenatally.
- Birthweight/ birthweight percentile
- Incidence of category 2 or 3 tracings
- Distribution of CPR by EFW
- Rate of operative vaginal delivery
- NICU admission
- Apgar scores at 1 and 5 minute
- Composite neonatal outcome

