9.5 SAMPLE SIZE

To determine sample size we assumed a 20% cesarean rate for those women who have a CPR <10th percentile and a 10% cesarean rate in women with a CPR ≥10th percentile. With 90% power to detect a difference and $\alpha = 0.05$, 288 subjects with a CPR <10th percentile will need to be enrolled into the study. This means approximately 3,000 subjects will need to be screened.

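### The synopsis and section 4.2.1 define different primary endpoints, and section 9.5 gives no rate or power for the one in the synopsis

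*Protocol*

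**What the plan says.** Four places in the protocol bear on the primary endpoint.

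- **Synopsis, endpoints.** The primary outcome is "Cesarean for non-reassuring fetal heart tracings". The first secondary outcome is "Total cesarean delivery rate".
- **Section 4.2.1.** "The primary endpoint is the cesarean delivery". No indication is attached.
- **Section 4.2.2.** The secondary list opens with "Total cesarean section rate".
- **Section 9.5.** The sample size rests on this statement: "we assumed a 20% cesarean rate for those women who have a CPR <10th percentile". The figure taken for the comparison group is 10%. Neither figure is tied to an indication.

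The stated purpose does not settle the matter. The synopsis objective asks whether women "with an abnormal CPR are more likely to be delivered by cesarean section", for whatever reason. Section 2.2 says that CPR measured near term "may predict which fetuses are at greatest risk for fetal distress in labor", but ends by referring to the need for cesarean in general. Section 2.1 cites a fourfold effect specifically on cesarean for fetal distress.

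**The concern.** Cesarean for non-reassuring tracings is a subset of all cesareans, so these are two outcomes with different event rates and, in all likelihood, different effect sizes. Both statements are current text, and the protocol does not say which prevails. An analysis plan could follow only one of them and would then contradict the other.

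Two things are at stake. First, the confirmatory claim is undefined: the same data could be significant on one endpoint and not on the other, and section 6.1.1 collects both mode of delivery and a fetal-compromise diagnosis, so either could be reported as primary. Second, if the synopsis governs, the rates in 9.5 are not rates of the primary endpoint.

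**Working it through.** **1. The texts side by side.**

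| Place | Indication-specific cesarean | Any cesarean |
|---|---|---|
| Synopsis, endpoints | primary | secondary |
| Section 4.2.1 | not mentioned | primary, as worded |
| Section 4.2.2 | not mentioned | secondary |
| Section 9.5 | no rate given | 20% v 10%, on the plain reading |

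Under 4.2 alone, any cesarean is both primary and secondary. Under the synopsis it is only secondary.

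**2. Reproducing the 288 in 9.5.** Inputs from 9.5: p1 = 0.20, p2 = 0.10, 90% power, α = 0.05. Two-sided testing and 1:1 groups are my assumptions. With mean rate 0.15 and d = 0.10:

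n = [1.960·√(2·0.15·0.85) + 1.282·√(0.20·0.80 + 0.10·0.90)]² / d² = 265.9, or 266 per group.

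With continuity correction: n′ = (n/4)·[1 + √(1 + 4/(n·d))]² = 285.5, or 286 per group.

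This is within two of the stated 288, so the figure is sound for 20% v 10% on whichever cesarean outcome was meant. It does not say which.

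**3. Power at the planned split.** Section 5.3 gives 3,000 women with about 300 below the 10th percentile, so 300 v 2,700. I used the pooled normal approximation, two-sided 0.05, without continuity correction:

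power = Φ[(|p1 − p2| − 1.960·s0)/s1], where s0 = √[p̄(1 − p̄)(1/300 + 1/2,700)], p̄ is the weighted mean rate, and s1 = √[p1(1 − p1)/300 + p2(1 − p2)/2,700].

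*At the rates in 9.5, 20% v 10%:* p̄ = 0.11, s0 = 0.0190, s1 = 0.0238. Power = Φ(2.63) = 99.6%.

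*Illustration.* Assume that CPR affects only the fetal-indication component, 6% v 3%, and that other cesareans run at 10% in both groups.
- Synopsis endpoint, 6% v 3%: p̄ = 0.033, s0 = 0.0109, s1 = 0.0141. Power = Φ(0.62) = 73%.
- Any cesarean, 16% v 13%: p̄ = 0.133, s0 = 0.0207, s1 = 0.0221. Power = Φ(−0.47) = 32%.

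This puts the comparison-group total at 13%, above the 10% in 9.5. Holding that total at 10% (3% fetal indication plus 7% other) makes any cesarean 13% v 10%: p̄ = 0.103, s0 = 0.0185, s1 = 0.0203. Power = Φ(−0.31) = 38%, so the gap from 73% remains.

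*Other assumed rates, with other cesareans at 10% in both groups:*

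| Fetal-indication rates, comparison v low CPR | Power, synopsis endpoint | Power, any cesarean |
|---|---|---|
| 2% v 4% | 59% | 18% (12% v 14%) |
| 3% v 9% | 99% | 79% (13% v 19%) |
| 2% v 8% (fourfold) | >99% | 81% (12% v 18%) |

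**4. The cited fourfold effect at a low base rate.** For 4% v 1%: p̄ = 0.013, s0 = 0.0069, s1 = 0.0115. Power on the synopsis endpoint = Φ(1.44) = 92%.

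**5. A doubling on the synopsis endpoint.** Power is 38%, 59%, 73%, 83% and 90% at assumed comparison rates of 1%, 2%, 3%, 4% and 5%.

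**The case against.** The strongest reply is that 4.2.1 is a shorthand that lost its qualifier. Total cesarean stays secondary in both the synopsis and 4.2.2, which makes sense only if the primary endpoint is something narrower. That is a fair inference and it guides the fix. It does not cure the text, because the synopsis objective and 9.5 also refer to cesarean without an indication.

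Four stronger readings are tempting, and the documents do not support them.

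- *The two endpoints could lead to opposite conclusions.* In every scenario above both move in the same direction. What differs is power, and so the chance of significance.
- *The study is underpowered.* The low figures come from assumed component rates. The 32% case uses a comparison-group total above the 10% in 9.5, and the smaller ratios leave out the only effect that the protocol cites. At that fourfold effect the synopsis endpoint has about 92% power even at a 1% base rate, and 20% v 10% has 99.6%.
- *The rationale fixes the endpoint as indication-specific.* Sections 2.1 and 2.2 speak both of fetal distress and of the need for cesarean in general. The rationale is mixed.
- *Section 9.5 expressly sizes the study on any cesarean.* That is its plain reading, but the section never names the endpoint.

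It may also be said that an analysis plan or registry entry names one endpoint. Neither is at hand, and neither would remove the contradiction inside the protocol.

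**Conclusion.** The protocol is wrong as written: two current passages define the primary endpoint differently, one variable is both primary and secondary under 4.2, and the synopsis endpoint has no assumed rate and no stated power. This rests on the text alone and needs no assumption.

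The practical size depends on rates that the protocol does not give. With 3% v 6% assumed for the fetal indication, power is 73% on one endpoint and 32% to 38% on the other, depending on whether other cesareans are taken as 10% or 7%. These figures show that the choice affects the result. They do not show a shortage of power. On the synopsis endpoint power falls short of 90% for a doubling if the comparison rate is below about 5%, but not for a fourfold effect at a rate of 1% or more.

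The point should be settled before outcomes are analysed, because it decides what the study can claim.

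**What to change.** 1. State one primary endpoint in identical words in the synopsis and 4.2.1, and name it in 9.5. The unchanged secondary listing of total cesarean favours the indication-specific endpoint. Because the objective and rationale are mixed, the investigators should confirm this. Either choice would remove the contradiction.
2. Remove the duplication, so that total cesarean appears in one tier only, and align the objective with the choice.
3. If the indication-specific endpoint is kept, define it from what is abstracted. Section 6.1.1 records a fetal-compromise diagnosis and the managing physician's diagnoses, which is not identical to cesarean for a non-reassuring tracing. The mapping should be written down.
4. Restate 9.5 with assumed rates and power for the chosen endpoint at the planned 300 v 2,700. For orientation, 90% power is available there for about 1% v 3.8%, 2% v 5.5%, 3% v 7.1% or 5% v 10.0%.

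The cost is wording in the synopsis, 4.2.1, 4.2.2, 6.1.1 and 9.5, with no new visit or measurement. The drawback is that the stated detectable difference or power may look less favourable than the present 90% for 20% v 10%.
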